## Introduction

Basketball is a contact sport that requires rapid and high-intensity movements such as jumping, changing direction, turning, landing, running (Sokoli, S. V., et al., 2024), Rubin, E. B., et al., 2021; Hannington, M. et al., 2022; Chang, L. L. Y., 2020). These maneuvers result in musculoskeletal injuries (Tummala, S. V., et al., 2022) and the highest frequency of knee injuries (Tummala, S. V., et al., 2022). Previous studies have shown the tendency to injure athletes in contact sports such as basketball (Qëndro et al., 2024). Young basketball players are influenced by the effects of continuous mechanical stress, rapid biological growth, sports overload, and neuromuscular development, which increases the risk of overuse injury (Zoellner, A., & Whatman, C., 2025) while limiting sports activities and functional limitations. In order to determine the impact of sports overuse injury, the sports population uses a measuring tool called the OSTRC Overuse Injury Questionnaire (Owoeye, O.B.A. et al., 2018). This is a standard questionnaire from the Oslo Sports Trauma Research Centre (Weiss, K. J., et al., 2017) to help identify injuries, especially in young athletes with symptoms. In many cases, in young athletes, not only are symptom monitoring, neuromuscular control, and dynamic stability evaluated, but also functional capacity. KOS-ADLS sports activity scale assesses the functional capacity of young basketball players in relation to the specific requirements of basketball (Nyland, J. et al. 2025). There are many conservative physiotherapeutic interventions to improve the functioning of young basketball players. Mulligan's technique is based on joint mobilization combined with active physiological movements and acts to interact with the physiological kinematics of joint movements and neurophysiological mechanisms of pain (ElMeligie, M. M., et al., 2025; Veizaj, S. S., et al., 2024). Randomized studies to assess the effect of Mulligan's MWM technique, versus Kinesiotaping and placebo, are limited, especially studies that are applied to young basketball players. The lack of evidence from randomized studies also has to do with the assessment of

the injury rate in young athletes, on the one hand, and the assessment of the level of activity and sports functionality, on the other. Although a good part of the research is focused on rehabilitation through conservative management of sports injury in young basketball players (Sos-Tirado, M. et al., 2024). This randomized study aimed to evaluate the effect of the Mulligan MWM technique, the Kinesiotaping technique, and a placebo intervention in young U16-U20 basketball players on reducing symptoms of knee injuries and improving functionality and sports levels. This study hypothesized that the Mulligan group would have a more significant improvement in the KOS-SAS and OSRTC scores.

### **Objectives**

The primary objective is to compare the effect of Mulligan, Kinesiotaping and Placebo in improving the functionality and scale of sports activity in U16-U20 basketball players.

The secondary objective is to evaluate the effect of the Mulligan, Kinesiotaping, and Placebo intervention in decreasing the level of overuse injuries in U16-U20 basketball players.

The third objective is whether each of the techniques, Mulligan, Kinesiotaping, and Placebo, has an impact on the relationship between decreasing the rate of OSTRC overuse injury and increasing the ADLS functional scale and SAS sports activity scale in U16-U20 basketball players.

### **Study Design**

This study was designed as a parallel group randomized controlled clinical trial with three intervention arms: Mulligan Mobilization with movement MWM, Kinesiotaping, and Placebo with repeated measurements at baseline, 1 hour, and 2 weeks after treatment.

### **Participants**

#### ***Inclusion Criteria:***

- ✓ Male and female genders
- ✓ Have a minimum of 2 years of sports experience
- ✓ Presence of knee injury
- ✓ Active participation in sport.

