#### ***Exclusion Criteria:***

- ✓ Knee surgery
- ✓ Knee instability
- ✓ Neurological disorders
- ✓ Not approve of the application of the Mulligan method

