## Interventions / Procedures

### *Mulligan Group Experimental*

For all participants who applied, regardless of the type of knee injury, Mulligan Mobilization with movement MWM in the squat position was used manually to maintain the homogeneity of the treatment. The intervention included tibial glide by the therapist while the basketball players actively performed the mobilization without pain. The athletes underwent the technique 2 sessions per week for 2 weeks. Each session lasted 5 min, and the technique was applied by a Physiotherapist who had the Mulligan technique certificate.

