### *Kinesiotaping Active Comparator Group*

Kinesiotaping was also used in a model regardless of the injury of athletes. Initially, the measurement was made from the medial and lateral condyles of the knee by placing a y-taping from the tibial tuberosity towards the femoral condyles, and another taping was placed horizontally over the patella. It was applied 2 times a week for 2 weeks for 5 minutes

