## Outcome Measures

Primary Outcomes:KOS-ADLS: The Activities of Daily Living Scale (ADLS) subscale of the Knee Outcome Survey evaluates symptoms and functional limitations during daily activities. Scores range from 0 to 100, with higher scores indicating better function.

The Sports Activity Scale (SAS) subscale of the Knee Outcome Survey evaluates knee function during sports and higher-level activities. Scores range from 0 to 100, with higher scores indicating better sports-related function.

Secondary outcomes The OSTRC Overuse Injury Questionnaire is a validated self-report tool used to monitor the severity and impact of overuse-related musculoskeletal problems. It assesses the consequences of knee-related problems on sports participation, training volume, performance, and symptom severity. Each question is scored on a graded response scale, and a severity score is calculated, with higher scores indicating greater symptom burden and functional impairment.

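### Objectives 2 and 3 claim a fall in the level and rate of overuse injury, but the trial measures only OSTRC severity in players with a knee injury of any onset

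*Protocol*

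**What the plan says.** - **Objectives (Protocol, Objectives).** The secondary objective is to evaluate the three interventions "in decreasing the level of overuse injuries in U16-U20 basketball players". The third asks whether each technique affects the relationship between "decreasing the rate of OSTRC overuse injury" and gains on ADLS and SAS.
- **Who enters (Protocol, Inclusion and Exclusion Criteria).** The only injury criterion is "Presence of knee injury". Players must also be active in their sport. The knee-specific exclusions are surgery and "Knee instability". Neither list mentions onset.
- **How they are treated (Protocol, Interventions / Procedures).** The Mulligan technique is given "regardless of the type of knee injury". For the taping arm the text reads "Kinesiotaping was also used in a model regardless of the injury of athletes".
- **What is measured (Protocol, Outcome Measures).** The OSTRC questionnaire is described as a tool to "monitor the severity and impact of overuse-related musculoskeletal problems". It yields a severity score on which higher is worse.
- **What is analysed (SAP, Objectives, Outcome Measures and Statistical Methods).** The OSTRC score is called ordinal and is taken at baseline and 2 weeks. The planned method is a mixed ANOVA of group by time, with no factor or subgroup for injury type.

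**The concern.** Two links between objective and data are missing.

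The first is the measure. A rate needs cases or new events set against a population or an amount of exposure. A severity score says how badly affected a player is, not how many players are affected or how often injuries arise.

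The second is the population. A conclusion about overuse injury needs players whose problem is overuse, or at least a way to separate them from the others. Here the injury type is left open at entry and deliberately ignored in treatment.

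At stake is the sentence that will be written at the end. A favourable OSTRC contrast could be reported as fewer overuse injuries, or as an effect on overuse injury in particular. Neither would follow from the data collected.

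**Working it through.** **1. The plan's own figure.** The only power statement (Protocol, Sample Size & Justification; SAP, Sample Size) is for ADLS. It reproduces: f = √(0.816 / 0.184) = 2.106, which rounds to the stated 2.11. With noncentrality f² × N = 0.816/0.184 × 60 = 266, 4 and 114 degrees of freedom and an assumed 5% level, power is 1.000, as stated. It says nothing about OSTRC.

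**2. Objective against measure.**

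| Needed for a claim about number or rate | In the documents |
|---|---|
| Definition of an overuse case, or a score cut-off | None |
| Count of new or recurrent injuries | None |
| Exposure or at-risk denominator | None |
| Players free of knee injury at entry | None: 60 of 60 must have one |
| Planned analysis of prevalence or incidence | None; the SAP compares scores |

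A lower mean score does not imply fewer cases. Suppose every player's score s is above 0 at baseline and falls to s/2. Mean severity drops by 50%, yet every s/2 is still above 0. The share with a problem is 100% before and 100% after.

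A prevalence of OSTRC problems could in principle be derived from the questionnaire, but neither document defines or plans one.

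**3. Objective against population.** Let q be the share of players whose injury is not overuse, d_o the treatment effect in overuse players and d_a the effect in the others. With q equal across arms, the whole-sample contrast is approximately

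(1 − q) × d_o + q × d_a.

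The documents give none of these three quantities. As an illustration, assume q = 0.5 and a whole-sample contrast of 0.5 SD. These pairs all fit:

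- d_o = 1.0, d_a = 0: 0.5 × 1.0 + 0.5 × 0 = 0.5
- d_o = 0, d_a = 1.0: 0.5 × 0 + 0.5 × 1.0 = 0.5
- d_o = d_a = 0.5: 0.5 × 0.5 + 0.5 × 0.5 = 0.5

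The planned analysis cannot tell an effect on overuse injury from an effect on other injuries. It does estimate the effect on OSTRC severity in the mixture enrolled.

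**4. What the score can address.** The Introduction words the aim as relief of knee-injury symptoms, and the SAP objective refers to OSTRC scores. Both fit a severity score. The mismatch lies in the wording of the protocol's objectives 2 and 3.

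**The case against.** The best defence is that this is mostly wording. Level of overuse injuries can fairly be read as severity, the SAP plans no rate analysis, and OSTRC is a secondary outcome. Broad eligibility with one standard technique per arm is a visible design choice. That defence largely stands for the word level. It does not rescue rate in the third objective, and it does not supply the overuse-specific population that both objectives name.

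A reader might also infer more than the documents support:

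- **That a favourable between-arm result could merely be recovery from acute injuries.** The trial is randomised with a placebo arm and is analysed by group and time. Spontaneous recovery is shared by the arms in expectation, and chance imbalance is what the significance level allows for. A positive contrast supports a treatment effect on OSTRC severity in those enrolled.
- **That acute injuries enter without limit.** Active participation is required, and surgery and instability are excluded, so some acute injuries are screened out. Milder ones can still qualify.
- **That many players score 0 at baseline and cannot improve.** The questionnaire covers symptoms as well as participation, training volume and performance. Nothing in the documents points to baseline zeros in injured players.
- **That dilution costs a known amount of power.** It depends on what is assumed for the other injuries. Take 20 per arm, an effect of 1.0 SD in overuse players and an unadjusted two-sided 5% t-test. With non-overuse shares of 20%, 30% and 50%, power is 69%, 58% and 34% if the others gain nothing, but 79%, 75% and 64% if they gain half as much. With no dilution at all it is 87%, or 74% at a Bonferroni level of 5%/3. The documents do not favour either assumption about the other injuries, so no power loss can be claimed.
- **That the main OSTRC analysis should be limited to overuse players.** On the zero-effect assumption, and at the same unadjusted 5% level, the remaining 16, 14 or 10 per arm have power of 78%, 72% or 56%. Under the half-effect assumption the whole sample does better at each share. Both documents already report an observed effect, so such a subset would be chosen after some outcome data had been analysed. It would also need an onset record that neither document shows to exist.

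**Conclusion.** The point holds as a limit on what may be concluded. The trial can compare arms on OSTRC severity in players with an existing knee injury. It cannot conclude that overuse injuries became fewer or less frequent, nor that an effect is specific to overuse injury. The fault is plain for rate in the third objective and milder for level in the second, where a severity reading is available.

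It touches two of the three objectives and one secondary outcome; ADLS and SAS are unaffected. No numerical size is attached, because the overuse share and the effects by onset are not given. The conclusion rests only on the documents' silence about onset, case definition and denominator, not on any assumed effect. It does not mean that the between-arm OSTRC comparison is biased or that eligibility has to change.

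**What to change.** 1. **Protocol, Objectives.** In the secondary and third objectives, replace the phrases about the level and the rate of overuse injury with: *OSTRC knee severity score in players with an existing knee injury*. The third objective then concerns how change in that score relates to change in ADLS and SAS.
2. **Reporting.** Make no claim about injury rate, or about overuse injury specifically, from the OSTRC result.
3. **If onset type was recorded before randomisation,** report the OSTRC result by onset (overuse versus acute) as a labelled exploratory analysis, and keep all randomised players as the main analysis. If it was not recorded, say so and stop at steps 1 and 2.

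The cost is a few words in the objectives, one optional exploratory table and a narrower claim. Eligibility, treatment and the main analysis set stay as they are.

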#### ***Exclusion Criteria:***

- ✓ Knee surgery
- ✓ Knee instability
- ✓ Neurological disorders
- ✓ Not approve of the application of the Mulligan method

### **Recruitment Method**

The basketball players were recruited from local sports clubs through referrals and collaborations from the club coaches.

## Interventions / Procedures

### *Mulligan Group Experimental*

For all participants who applied, regardless of the type of knee injury, Mulligan Mobilization with movement MWM in the squat position was used manually to maintain the homogeneity of the treatment. The intervention included tibial glide by the therapist while the basketball players actively performed the mobilization without pain. The athletes underwent the technique 2 sessions per week for 2 weeks. Each session lasted 5 min, and the technique was applied by a Physiotherapist who had the Mulligan technique certificate.

### *Kinesiotaping Active Comparator Group*

Kinesiotaping was also used in a model regardless of the injury of athletes. Initially, the measurement was made from the medial and lateral condyles of the knee by placing a y-taping from the tibial tuberosity towards the femoral condyles, and another taping was placed horizontally over the patella. It was applied 2 times a week for 2 weeks for 5 minutes

### *Placebo Comparator Group*

In this group, participants received a sham intervention to mimic the treatment without therapeutic effect twice a week for 2 weeks, for 5 minutes.

## Outcome Measures

Primary Outcomes:KOS-ADLS: The Activities of Daily Living Scale (ADLS) subscale of the Knee Outcome Survey evaluates symptoms and functional limitations during daily activities. Scores range from 0 to 100, with higher scores indicating better function.

The Sports Activity Scale (SAS) subscale of the Knee Outcome Survey evaluates knee function during sports and higher-level activities. Scores range from 0 to 100, with higher scores indicating better sports-related function.

Secondary outcomes The OSTRC Overuse Injury Questionnaire is a validated self-report tool used to monitor the severity and impact of overuse-related musculoskeletal problems. It assesses the consequences of knee-related problems on sports participation, training volume, performance, and symptom severity. Each question is scored on a graded response scale, and a severity score is calculated, with higher scores indicating greater symptom burden and functional impairment.

## Timeline / Schedule of Assessments

Outcome /Assessment	Baseline treatment	pre	1 hour post treatment	2 weeks post treatment
KOS-ADLS ; ADLS	*		*	*
SAS	*		*	*
OSTRC	*		*	*`

## Sample Size & Justification

The simple size (N=60) was determined based on the available number of eligible participants during the period of study. A post-hoc power analysis was conducted for the

ADLS outcome using mixed ANOVA. The time  $\times$  group interaction yielded  $\eta^2p = 0.816$  (Cohen's  $f = 2.11$ ), indicating a very high statistical power (1.0) for detecting the observed effect.

### **Ethics and Regulatory Approvals**

Ethics Committee Approval. This study has been reviewed and approved by the University of Sports of Tirana. Ethics Committee for scientific research.

Approval Reference Number: Prot. Nr. 3736/2

Approval Date: 10/12/2024.

### **Confidentiality Measures**

All participant data will be treated with strict confidentiality. Personal identifiers have been replaced with coded identification numbers. Data are stored and are only accessible by the study researchers. Any publication or presentation of study results will report only aggregated data, ensuring that individual participants cannot be identified.

### **Introduction / Objectives**

This Statistical Analysis Plan (SAP) outlines the predefined statistical methods that will be applied to analyze the data collected in this RTC comparing Mulligan with mobilization MWM, Kinesiotaping, and Placebo interventions in U16–U20 basketball players. The SAP ensures transparency, reproducibility, and consistency in the evaluation of study outcomes.

### **Objectives**

The primary objective of this SAP is to define the statistical approach for assessing differences between groups and over time, functional outcomes ADLS and SAS, and overuse injury scores (OSTRC) across the three study groups and time points.

### **Study Design**

The present study will be designed as a parallel group randomized controlled clinical trial with three intervention arms: Mulligan mobilization MWM, kinesiotaping, and placebo, with repeated measurements at baseline, 1 hour, and 2 weeks of follow-up. The study will be conducted over a two- week intervention period as a part of a doctoral research project. The study will be carried out with CONSORT reporting guidelines (Schulz, K.F. et al., 2010)

### **Sample Size**

The sample size was calculated using G \*power- 3.1 software (Faul, F. et al., 2007) while we used the actual sample size (N=60) and conducted post-hoc power analysis for the primary outcome, ADLS, and mixed ANOVA. Interaction was  $\eta^2p = 0.816$  (Cohen's  $f = 2.11$ ), and the statistical power indicated a very high (1.0).

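### The stated power of 1.0 is observed power from the trial's own ADLS result; it does not justify N=60, the two documents differ on how N was set, and no prospective power is established

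*SAP*

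**What the plan says.** The Protocol (Sample Size & Justification) states that N=60 "was determined based on the available number of eligible participants during the period of study". It then reports a post-hoc analysis of ADLS by mixed ANOVA, with a time by group interaction of partial eta-squared 0.816 (f 2.11), "indicating a very high statistical power (1.0) for detecting the observed effect".

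The SAP (Sample Size) begins "The sample size was calculated using G", followed by the rest of the program name (G\*Power 3.1). The same sentence goes on to say that the actual sample of 60 was used and that the authors "conducted post-hoc power analysis for the primary outcome, ADLS, and mixed ANOVA". It repeats 0.816, 2.11 and 1.0, but without the Protocol's qualifier "for detecting the observed effect".

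Neither document gives a planning effect, an SD, alpha, a target power, an allocation ratio or a dropout allowance. Neither gives a power figure for SAS or OSTRC. The SAP introduction describes its methods as predefined, yet its sample-size section contains the interaction result for ADLS.

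**The concern.** A sample-size section should show what the design could detect before any results were known. A power computed from the effect that the trial itself produced cannot do that. It is a function of the test statistic already obtained, so a very significant result always returns a power near 1.

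The figure also covers only one of the trial's questions. It concerns the omnibus ADLS interaction. The hypothesis at the end of the Protocol's introduction is that Mulligan improves KOS-SAS and OSTRC scores more than the other arms. The Protocol lists SAS with ADLS under primary outcomes. The comparisons that show which arm is better are the Bonferroni-adjusted post-hoc contrasts in the SAP's Statistical Methods. The 1.0 applies to none of these. A reader who carries it over to them could take a non-significant contrast, such as Mulligan against kinesiotaping, as evidence of no difference.

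The accounts of N also need to agree. A number fixed by availability and a number obtained by calculation are different justifications, and only the first is backed by anything shown.

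**Working it through.** **Inputs from the documents.** N = 60; 3 arms; 3 time points for ADLS; partial eta-squared 0.816; f 2.11; stated power 1.0.

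**Assumptions, because the documents are silent.** Alpha 0.05 (two-sided for pairwise tests); 20 per arm; sphericity unless stated otherwise.

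**1. Reproduce the plan's figures.**
- f = sqrt(0.816 / (1 − 0.816)) = sqrt(0.816 / 0.184) = 2.106, which rounds to the stated 2.11.
- Interaction degrees of freedom: (3 − 1)(3 − 1) = 4 and (60 − 3)(3 − 1) = 114.
- Implied F = (0.816 / 4) / (0.184 / 114) = 126.4, with p about 6 × 10⁻⁴¹.
- Noncentrality on the partial eta-squared scale: f² × 114 = 505.6. The critical F(4,114) is 2.45, and power is 1.000.
- Other conventions for the noncentrality, with within-person correlation 0 to 0.8 and sphericity epsilon 0.5 or 1, give values from 133 to 3991. Power is 1.000 in every case.

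The stated 1.0 is therefore arithmetically correct for f = 2.11.

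**2. What that figure carries.** On the partial eta-squared scale, observed power is fixed by F and its degrees of freedom. An interaction with p exactly 0.05 has F = 2.45, so partial eta-squared = (4 × 2.45) / (4 × 2.45 + 114) = 0.079, and observed power is 0.69. Any f of about 0.51 or more returns at least 0.995. The 1.0 adds nothing to the test result.

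**3. Interaction power at N=60 without using the results.** Power = P(noncentral F(4,114) > 2.45), with noncentrality f² × 114:

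| f (partial eta-squared scale) | Power |
|---|---|
| 0.10 | 0.11 |
| 0.25 | 0.53 |
| 0.33 | 0.80 |
| 0.40 | 0.94 |

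The scale of f matters. With noncentrality f² × N × 3 / (1 − rho), 80% power needs f of about 0.26, 0.19 and 0.12 for rho of 0, 0.5 and 0.8. Any replacement statement must say which scale it uses.

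**4. Two arms compared at one time point.** Noncentral t, df = 38, noncentrality d × sqrt(20 / 2):

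| | Alpha 0.05 | Alpha 0.05/3 (three pairs) |
|---|---|---|
| d for 80% power | 0.91 | 1.06 |
| Power at d = 0.5 | 0.34 | 0.19 |
| Power at d = 0.8 | 0.69 | 0.52 |

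The SAP does not state the size of the Bonferroni family, so three pairs is an assumption.

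**5. The two accounts of N.** The Protocol gives availability. The SAP gives a calculation, but describes an analysis that is post hoc and takes the achieved 60 as its input. An analysis that starts from N cannot have produced N.

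**The case against.** The strongest defence is that the Protocol is open about what was done: it calls the analysis post hoc and limits the power to the observed effect. That stands. A reader might infer that the plan claims a power the design lacks, or that the 1.0 is a miscalculation. The documents support neither reading. At f = 2.11 the power is 1.0, and the supportable statement is only that no prospective power has been established. Depending on an effect that nobody specified, it could be low or high.

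It can also be said that the SAP's sentence, read whole, means that G\*Power was used only for the post-hoc step, which fits availability as the basis for N. That is plausible, and it makes the conflict one of wording. But the sentence as written asserts a sample-size calculation, so it still needs correcting.

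A further temptation is to set the stated 100% directly against 19% or 34% for a pairwise contrast. These are different quantities: one is an omnibus interaction at the observed effect, the others are two-sample tests at assumed effects. Neither document claims pairwise power. The power of a pairwise contrast in change from baseline would also depend on a within-person correlation that is not given. The pairwise figures show what the 1.0 leaves unanswered; they do not contradict it.

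Finally, both sections name ADLS only, and no null contrast is reported, so misreading of null findings is a risk and not something the documents show has happened.

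**Conclusion.** The point holds as a defect of justification and wording, not of arithmetic. The 1.0 is observed power for the ADLS interaction. It gives no support for N=60 and no information on SAS, OSTRC or the adjusted pairwise contrasts. The SAP's statement that the sample size was calculated conflicts with the Protocol and is not backed by any planning input.

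On size: with N=60 and alpha 0.05, the interaction needs f of about 0.33 on the partial eta-squared scale for 80% power, that is, a partial eta-squared of 0.33² / (1 + 0.33²) = 0.098. With 20 per arm, a two-arm comparison at one time point needs about 0.91 SD, or 1.06 SD with Bonferroni over three pairs. Alpha, equal allocation, the number of pairs and no dropout are assumptions, and the interaction figure also assumes sphericity. The finding that no prospective power is stated depends on none of them.

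**What to change.** - **SAP, Sample Size:** delete the statement that the sample size was calculated in G\*Power. Say, as the Protocol already does, that N=60 was set by the number of eligible participants available.
- **Both sample-size sections:** remove the observed effect (0.816, 2.11) and the power of 1.0. The interaction estimate belongs with the results.
- **Both sections:** insert a detectable-difference statement that does not use the results and labels its assumptions, for example: *Assuming 20 per arm and two-sided alpha 0.05, a two-arm comparison at one time point has 80% power for a difference of about 0.91 SD, or about 1.06 SD if Bonferroni-adjusted for three pairs. For the group by time interaction, 80% power needs f of about 0.33 on the partial eta-squared scale.* The sponsor should replace the assumed allocation, alpha and number of pairs with the actual ones if they differ.
- **SAP, Statistical Methods:** report group differences with 95% confidence intervals, and state that a non-significant contrast will not be read as no difference.

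The cost is wording, chiefly the two sample-size paragraphs, and a less favourable stated figure. No further participants are needed.
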